7.0 Study Withdrawal/Discontinuation

Participants may withdraw consent to participate in this study at any time. They also have the right to cancel permission to use and disclose further information collected about the child, in writing, at any time. If they cancel permission to use the child's information, the researchers will stop collecting additional information. However, the research team may use and disclose information that was gathered before they received the cancellation.

Assent is determined by demonstrating activities to the participants and asking if they want to participate. If a participant indicates he or she does not want to participate (though verbal and/or nonverbal means), the principal investigator or research assistant offers a break and then invites the participant to engage in the activity again. If the child continues to verbally and/or nonverbally (e.g., running away or crying) indicate he or she does not want to participate after three consecutive attempts to re-engage, the intervention is discontinued for that session. If a child declines to participate during three consecutive sessions, we will discontinue intervention with that participant and discuss that discontinuation with his or her caregivers.

8.0 Statistical Considerations

Visual Analysis

Visual analysis is the primary analysis method for single case research design (Ledford & Gast, 2018). Consistent with What Works Clearinghouse practices, we consider five features of the data pattern: level, trend, variability, overlap, and consistency (Kratochwill et al., 2010). We use visual analysis to determine whether there is functional relation between the independent variable (i.e., specific retrieval practice component) and the dependent variable. For each participant with the relevant conditions in their contrast, we examine whether there is evidence of a functional relation between the independent variable and dependent variable. We combine across participants based on the What Works Clearinghouse criteria for strong, moderate, and no evidence of an effect (What Works Clearinghouse, 2016).

Research questions related to effectiveness of the active interventions (i.e., RQs 1-4 and 7-10) will be judged based on accuracy for words taught in the active intervention condition versus those in the no-teaching condition. Research questions related to efficiency (i.e., RQs 5, 6, 11, and 12) will be judged based on accuracy for words taught in one active condition versus those taught in the other (e.g., retrieval practice with versus without feedback).

Feedback. Participants ($n = 8$) in Contrasts A (feedback vs. no feedback with massed trials) and B (feedback vs. no feedback with spaced trials) address the effect of feedback (see Figure 1). Table 2 displays how we will compare conditions within Contrasts A and B to evaluate both effectiveness and efficiency research questions. For all of these analyses, we use expressive labeling as the primary dependent variable. Therefore, performance for expressive labeling determines when phases change. Phonological precision, receptive performance, and knowledge of semantic content (i.e., location) are secondary variables that will be considered when interpreting the overall results. For example, one condition may exhibit greater accuracy for the primary dependent variable, but not for one or more of the secondary variables.

Figure 1
Study Contrasts

	Feedback	No feedback	Contrasts to Determine Effect of Feedback (RQs 1-6)
Massed	Feedback with massed trials	No feedback with massed trials	Contrast A: Feedback vs. no feedback (massed trials)
Spaced	Feedback with spaced trials	No feedback with spaced trials	Contrast B: Feedback vs. no feedback (spaced trials)
Contrasts to Determine Effect of Spacing (RQs 7-12)	Contrast D: Spaced vs. massed trials (with feedback)	Contrast C: Spaced vs. massed trials (no feedback)	

Table 2. *Comparisons of Relevant Conditions for the Effect of Feedback*

Research question		Contrast	Condition 1	Condition 2	Phase	Feedback RQs
Effectiveness or efficiency	Acquisition or retention					
Effectiveness	Acquisition	A	Feedback w/massed trials	No-teaching control	Comparison	1
		B	Feedback w/spaced trials	No-teaching control	Comparison	1
		A	No feedback w/massed trials	No-teaching control	Comparison	2
		B	No feedback w/spaced trials	No-teaching control	Comparison	2
Effectiveness	Retention	A	Feedback w/massed trials	No-teaching control	Maintenance	3
		B	Feedback w/spaced trials	No-teaching control	Maintenance	3
		A	No feedback w/massed trials	No-teaching control	Maintenance	4
		B	No feedback w/spaced trials	No-teaching control	Maintenance	4
Efficiency	Acquisition	A	Feedback w/massed trials	No feedback w/massed trials	Comparison	5
		B	Feedback w/spaced trials	No feedback w/spaced trials	Comparison	5
Efficiency	Retention	A	Feedback w/massed trials	No feedback w/massed trials	Maintenance	6
		B	Feedback w/spaced trials	No feedback w/spaced trials	Maintenance	6

Effectiveness. For research questions related to effectiveness, we determine whether there is an increase in accuracy for the active retrieval practice condition without an

accompanying increase, or with a smaller increase, for the no-teaching control condition. Given that the target words are novel words, participants are not expected to show increased accuracy for the dependent variables for the control condition.

For effectiveness of retrieval practice with feedback for *acquisition* (RQ1), we determine whether there is a separation of the data paths (as indicated by visual analysis and statistical analyses) for (a) the retrieval practice with feedback with massed trials condition and the no-teaching control condition and (b) the retrieval practice with feedback with spaced trials condition and the no-teaching control condition in the comparison phase. This separation of the data paths with the retrieval practice condition above the no-teaching condition in the comparison phase would provide evidence of the effectiveness of retrieval practice with feedback.

For effectiveness of retrieval practice without feedback for *acquisition* (RQ2), we determine whether there is a separation of the data paths for (a) the retrieval practice without feedback with massed trials condition and the no-teaching control condition and (b) the retrieval practice without feedback with spaced trials condition and the no-teaching control condition in the comparison phase. This separation of the data paths with the retrieval practice condition above the no-teaching condition in the comparison phase would provide evidence of the effectiveness of retrieval practice without feedback.

For effectiveness of retrieval practice with feedback for *retention* (RQ3), we determine whether there is a separation of the data paths for (a) the retrieval practice with feedback with massed trials condition and the no-teaching control condition and (b) the retrieval practice with feedback with spaced trials condition and the no-teaching control condition in the maintenance phase. This separation of the data paths with the retrieval practice condition above the no-teaching condition in the maintenance phase would provide evidence of the effectiveness of retrieval practice with feedback for retention.

For effectiveness of retrieval practice without feedback for *retention* (RQ4), we determine whether there is a separation of the data paths for (a) the retrieval practice without feedback with massed trials condition and the no-teaching control condition and (b) the retrieval practice without feedback with spaced trials condition and the no-teaching control condition in the maintenance phase. This separation of the data paths with the retrieval practice condition above the no-teaching condition in the maintenance phase would provide evidence of the effectiveness of retrieval practice without feedback for retention.

Efficiency. For research questions related to efficiency, we determine whether there is faster attainment of the mastery criterion for one retrieval practice condition versus another and whether mastery-level performance is better maintained.

For efficiency of retrieval practice with versus without feedback for *acquisition* (RQ5), we determine whether there is a separation of the data paths for (a) the retrieval practice with feedback with massed trials condition and the retrieval practice without feedback with massed trials condition (Contrast A) and (b) the retrieval practice with feedback with spaced trials condition and the retrieval practice without feedback with spaced trials condition (Contrast B) in the comparison phase. The number of sessions to mastery is

also considered when determining the presence of a functional relation related to efficiency. This separation of the data paths in the comparison phase would provide evidence of greater efficiency for the condition with the path that is displayed higher on the graph.

For efficiency of retrieval practice with versus without feedback for *retention* (RQ6), we determine whether there is a separation of the data paths for (a) the retrieval practice with feedback with massed trials condition and the retrieval practice without feedback with massed trials condition (Contrast A) and (b) the retrieval practice with feedback with spaced trials condition and the retrieval practice without feedback with spaced trials condition (Contrast B) in the maintenance phase. The number of sessions to fall below mastery is also considered when determining the presence of a functional relation related to efficiency. This separation of the data paths in the maintenance phase would provide evidence of greater efficiency for the condition with the path that is displayed higher on the graph.

Spacing. Participants ($n = 8$) in Contrasts C (spaced vs. massed trials without feedback) and D (spaced vs. massed trials with feedback) address the effect of spacing. Table 3 displays how we will compare conditions within Contrasts C and D to evaluate both effectiveness and efficiency research questions. As with the analyses for feedback, we use expressive labeling as the primary dependent variable. Phonological precision, receptive performance, and knowledge of semantic content are secondary variables that will be considered when interpreting the overall results.

Table 3. *Comparisons of Relevant Conditions for the Effect of Spacing*

Research question		Contrast	Condition 1	Condition 2	Phase	Spacing RQs
Effectiveness or efficiency	Acquisition or retention					
Effectiveness	Acquisition	C	No feedback w/spaced trials	No-teaching control	Comparison	7
		D	Feedback w/spaced trials	No-teaching control	Comparison	7
		C	No feedback w/massed trials	No-teaching control	Comparison	8
		D	Feedback with massed trials	No-teaching control	Comparison	8
Effectiveness	Retention	C	No feedback w/spaced trials	No-teaching control	Maintenance	9
		D	Feedback w/spaced trials	No-teaching control	Maintenance	9
		C	No feedback w/massed trials	No-teaching control	Maintenance	10
		D	Feedback with massed trials	No-teaching control	Maintenance	10
Efficiency	Acquisition	C	No feedback w/massed trials	No feedback w/spaced trials	Comparison	11
		D	Feedback w/massed trials	Feedback w/spaced trials	Comparison	11
Efficiency	Retention	C	No feedback w/massed trials	No feedback w/spaced trials	Maintenance	12
		D	Feedback w/massed trials	Feedback w/spaced trials	Maintenance	12

Effectiveness. For research questions related to effectiveness, we determine whether there is an increase in accuracy for the active retrieval practice condition without an accompanying increase, or with a smaller increase, for the no-teaching control condition. Given that the target words are novel words, participants are not expected to show increased accuracy for the dependent variables for the control condition.

For effectiveness of retrieval practice with spaced trials for *acquisition* (RQ7), we determine whether there is a separation of the data paths for (a) the retrieval practice without feedback with spaced trials condition and the no-teaching control condition and (b) the retrieval practice with feedback with spaced trials condition and the no-teaching control condition in the comparison phase. This separation of the data paths with the retrieval practice condition above the no-teaching condition in the comparison phase would provide evidence of the effectiveness of retrieval practice with spaced trials.

For effectiveness of retrieval practice with massed trials for *acquisition* (RQ8), we determine whether there is a separation of the data paths for (a) the retrieval practice without feedback with massed trials condition and the no-teaching control condition and (b) the retrieval practice with feedback with massed trials condition and the no-teaching control condition in the comparison phase. This separation of the data paths with the retrieval practice condition above the no-teaching condition in the comparison phase would provide evidence of the effectiveness of retrieval practice with massed trials.

For effectiveness of retrieval practice with spaced trials for *retention* (RQ9), we determine whether there is a separation of the data paths for (a) the retrieval practice without feedback with spaced trials condition and the no-teaching control condition and (b) the retrieval practice with feedback with spaced trials condition and the no-teaching control condition in the maintenance phase. This separation of the data paths with the retrieval practice condition above the no-teaching condition in the maintenance phase would provide evidence of the effectiveness of retrieval practice with spaced trials for retention.

For effectiveness of retrieval practice with massed trials for *retention* (RQ10), we determine whether there is a separation of the data paths for (a) the retrieval practice without feedback with massed trials condition and the no-teaching control condition and (b) the retrieval practice with feedback with massed trials condition and the no-teaching control condition in the maintenance phase. This separation of the data paths with the retrieval practice condition above the no-teaching condition in the maintenance phase would provide evidence of the effectiveness of retrieval practice with massed trials for retention.

Efficiency. For research questions related to efficiency, we determine whether there is faster attainment of the mastery criterion for one retrieval practice condition versus another and whether mastery-level performance is better maintained.

For efficiency of retrieval practice with spaced versus massed trials for *acquisition* (RQ11), we determine whether there is a separation of the data paths for (a) the retrieval practice without feedback with massed trials condition and the retrieval practice without feedback with spaced trials condition (Contrast C) and (b) the retrieval practice

with feedback with massed trials condition and the retrieval practice with feedback with spaced trials condition (Contrast D) in the comparison phase. The number of sessions to mastery is also considered when determining the presence of a functional relation related to efficiency. This separation of the data paths in the comparison phase would provide evidence of greater efficiency for the condition with the path that is displayed higher on the graph.

For efficiency of retrieval practice with spaced versus massed trials for *retention* (RQ12), we determine whether there is a separation of the data paths for (a) the retrieval practice without feedback with massed trials condition and the retrieval practice without feedback with spaced trials condition (Contrast C) and (b) the retrieval practice with feedback with massed trials condition and the retrieval practice with feedback with spaced trials condition (Contrast D) in the maintenance phase. The number of sessions to fall below mastery is also considered when determining the presence of a functional relation related to efficiency. This separation of the data paths in the maintenance would provide evidence of greater efficiency for the condition with the path that is displayed higher on the graph.

Statistical Analysis

There is no consensus on recommended statistical analyses for single case research designs, particularly for the adapted alternating treatments design, which is underrepresented in research on the use of statistical analyses and effect sizes in single case research. We will calculate Nonoverlap of All Pairs (NAP; Parker & Vannest, 2009), an overlap-based effect size, and analyze differences in conditions analogous to those described for visual analysis. Because overlap is one feature used for determining a functional relation, NAP will provide guidance on the degree of confidence for inferring the amount of overlap between conditions. NAP is defined as the number of comparison pairs between phases A and B without overlap divided by the total comparisons. It is related to Tau, another overlap metric. Tau is a linear re-scaling of NAP (Zimmerman et al., 2018). NAP offers several advantages over other overlap-based effect sizes, including less human error in calculations (can be calculated by hand or via computerized methods), stronger validation by R^2 , and narrower confidence intervals (Parker & Vannest, 2009). Parker and Vannest (2009) tentatively suggest the following guidelines for NAP effect sizes: .93 – 1.00 = large, .66 – .92 = medium, and 0 – .65 = weak.

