Because the AATD requires sets of equal difficulty, the word sets are made of novel words balanced for number of phonemes and syllables, phonotactic probability, and lexical neighborhood density (Storkel, 2003; Storkel & Hoover, 2010a, 2010b). Novel words nearly eliminate the possibility of prior exposure and enable the creation of balanced word sets. Early developing consonants and tense vowels expected to be in the participants' phonemic repertoires (assessed prior to baseline) are primarily used, which aids acquisition receptively and expressively (Leonard et al., 1982). Words do not contain high frequency phonemes (based on acoustic frequency) because they influence word learning and are more likely to be less audible, inaudible, or distorted than lower frequency phonemes for DHH children (Niskar et al., 1998; Shargorodsky et al., 2010; Stelmachowicz et al., 2004b). The following words sets are used: (1) /zod/, /wam/, /getʃ/, and /pib/; (2) /pem/, /vad/, /jotʃ/, and /kub/; (3) /jum/, /tetʃ/, /vob/, and /ked/.

Unfamiliar Objects

Each novel word is randomly paired to an unfamiliar object (e.g., building sets and hardware store items). Testing prior to baseline ensures that participants do not have a consistent form associated with any unfamiliar object or a meaning associated with any of the novel words.

Semantic Content

During intervention the examiner labels the novel object's location (e.g., toy box or bathtub) to increase semantic content. Including this content provides an early step towards using retrieval practice to teach rich vocabulary content that is necessary for achieving age expected language skills without threatening the study's internal validity. Locations are randomly assigned to avoid objects' perceptual features being associated with locations and pretested to ensure participants have the conceptual knowledge of each location to maintain balanced word sets across conditions.

Procedures

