All sessions are in-person and videorecorded. Participants must pass a listening check to proceed with the session. Sessions take place in a quiet room (ambient noise ≤ 40 dB as measured by a sound level mobile application) in the child's home, educational setting, or clinic, depending on caregiver preference. Flexibility in location to match caregiver preferences is one way we guard against attrition. Having the examiner for all assessments and intervention sessions be a research team member, rather than school personnel, and conducting the intervention for a relatively short period of time are also designed to guard against attrition.

Dependent Variable Probe

The dependent variable probes (about 10 minutes) test the 12 target words in sets by condition. The primary dependent variable is the percent accuracy (i.e., correct responses / total trials x 100) for labeling target words expressively. The examiner asks the child to label the taught unfamiliar objects and one known object per set (i.e., "What's this?"). The participant is given up to 10 seconds to respond. The secondary dependent variables are the percent accuracy for (a) receptively identifying target words within 5 seconds in a field of six (i.e., four target objects, one foil, and a known object), (b) associated semantic information (i.e., location; "Where's this from?"), and (c) phonological precision for labeling target words expressively. The examiner will not provide any feedback regarding response accuracy for target words during the dependent variable probes. To maintain engagement, the examiner may provide positive reinforcement for non-target behaviors and for identifying the known word for each group, which is expected to be particularly important in the early sessions when accuracy for target words is expected to be low. The study's procedural manual specifies how the examiner should respond to specific child behaviors (e.g., self-corrections and articulatory errors). Primary and secondary coders double enter data into an electronic form using direct systematic observation of the video recordings (Ledford & Gast, 2018).

A research assistant codes at least 25% of sessions in each condition for each participant for interobserver agreement (IOA). The primary coder is blind to which sessions are coded for reliability. All coders are trained to .85 point-by-point agreement for independent coding of three consecutive sessions via recordings of non-participants

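### For the secondary location outcome, separation from the untaught control does not by itself distinguish object-place learning from guessing among familiar places heard only in lessons

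*Combined protocol and SAP*

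**What the plan says.** Under Dependent Variable Probe (section 5.0), one secondary outcome is percent accuracy for "associated semantic information", obtained by an open question about where the object comes from. It is asked for all 12 words, set by set. No response options, chance level or error analysis are given for it.

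Under Semantic Content (section 5.0): "During intervention the examiner labels the novel object's location (e.g., toy box or bathtub) to increase semantic content". On how places are chosen: "Locations are randomly assigned to avoid objects' perceptual features being associated with locations". They are also "pretested to ensure participants have the conceptual knowledge of each location to maintain balanced word sets across conditions". The number of places, and whether the three sets draw on the same ones, is not stated.

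In Table 1 each taught word has its place stated once and then three more times, with two retrieval prompts for the place and one further prompt at the end of the set. Control words receive no teaching.

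Under Visual Analysis (section 8.0), effectiveness questions (RQs 1-4 and 7-10) "will be judged based on accuracy for words taught in the active intervention condition versus those in the no-teaching condition". The Effectiveness paragraphs accept either no rise in control or a smaller rise than in the active condition. They add: "Given that the target words are novel words, participants are not expected to show increased accuracy for the dependent variables for the control condition". That sentence appears under both Feedback and Spacing. Location is a secondary variable, used to interpret the overall results.

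**The concern.** The stated reason for a flat control is that the words are new. To answer the location question, a child needs no new word, only a familiar place name. After the first lessons the child has rehearsed a short list of places for taught objects and has had no such rehearsal for control objects. A child who remembers the list, but not which object goes with which place, will sometimes be right on taught objects. Unless control objects happen to share those places, the same child will almost never be right on control objects.

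The receptive task is different: its field of six gives every set the same options. Baseline cannot reveal the problem either, because no place has yet been taught.

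What is at stake is a modest separation on location being reported as object-place learning. Section 8.0 itself gives the example of secondary variables that do not follow the primary, so a location result could colour the interpretation.

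**Working it through.** The documents give no chance level or expected accuracy for location, so there is no figure to reproduce.

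**Inputs from the documents.** Three sets of four words (3 × 4 = 12), of which two are taught (8 words) and one is control (4 words). NAP bands in section 8.0, Statistical Analysis: medium .66-.92, weak up to .65.

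**Assumptions, not stated in the documents.** One location trial per word per probe; each object in a set has its own place; the child always answers with a lesson place and has no object-place pairing knowledge.

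**Case 1: control places are not among the lesson places.** Control accuracy is 0%. With X correct out of four in a taught set, NAP with ties counted half is P(X ≥ 1) + 0.5 × P(X = 0) = 0.5 + 0.5 × P(X ≥ 1). Without tie credit it is P(X ≥ 1).

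| How the child guesses | Mean accuracy | P(X ≥ 1) | NAP, ties half | NAP, no tie credit |
|---|---|---|---|---|
| Among the 8 lesson places | 12.5% | 1 − (7/8)^4 = .414 | .71 | .41 |
| One-to-one within the set's 4 places | 25% | 15/24 = .625 | .81 | .625 |
| Independently within the set's 4 places | 25% | 1 − (3/4)^4 = .684 | .84 | .68 |

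Both 25% rows presume that the child knows which four places belong to the set being probed. Only the 12.5% row needs nothing beyond the list. The plan defines NAP without saying how ties are treated. With half credit all three values are in the medium band; without it only .68 is.

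Over 10 sessions, the chance that the taught mean exceeds a zero control is 1 − (7/8)^40 = .995 at the lower guessing rate, and higher at the other.

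**Case 2: partial sharing, guessing among 8 places (binomial approximation, ties half).**
- One of four control places shared: control mean 1/8 × 1/4 = 3.1%, against 12.5% taught; NAP .65.
- Two of four shared: control mean 1/8 × 2/4 = 6.25%, against 12.5% taught; NAP .60.

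Both values are weak, but the control rise is still the smaller one, which the effectiveness rule accepts.

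**Case 3: the same four places in every set.** 25% against 25%, NAP .50. There is no bias.

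**How far guessing can reach.** With independent guesses, at least 3 of 4 correct in one session has probability .007 (rate 1/8) to .051 (rate 1/4). Guessing therefore produces a low plateau and not mastery-level accuracy.

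**The proposed reference line.** Pair the child's four answers with the four objects in all 24 ways. Each answer meets each object in 6 of the 24. If k answers name a place belonging to that set, the average number of matches is k × 6/24 = k/4, which is k/16 of the four trials. The line is 25% at k = 4, 12.5% at k = 2 and 0% at k = 0. It equals the accuracy expected from those same answers without pairing knowledge, whichever place pool was used.

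**The case against.** The strongest reply is that the bias rests on a fact the documents do not contain. Places are assigned at random and pretested; nothing says the control set has different ones. With a common pool the control is a fair guessing reference, and pretesting each place might also expose children to the control places. The procedural manual may settle this, but it is not available here. This stands, so the size is conditional.

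A reader might infer that the sentence on novel words is false. The documents do not support that: with a control at 0%, as in case 1, its prediction of no increase comes true. The gap is that a flat control does not show that accuracy on taught sets reflects pairing knowledge.

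A reader might also blame familiarity of the places alone. The mechanism is unequal exposure to the list of answers. A child who had learned the taught labels but not their objects would gain in the same way on expressive labeling. Familiarity lets it act from the first lesson.

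It is also fair that a child who hears each place four times and is asked for it three times per session will probably learn some pairings, that visual analysis weighs level and trend as well as overlap, and that the two active conditions have similar place exposure while both are taught. These points limit the practical effect. They do not supply the missing guessing reference.

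**Conclusion.** The point holds as a limited one. For location, separation from the untaught control is not sufficient evidence of object-place learning, and the novelty of the words does not fill that gap. If control and lesson places do not overlap, guessing alone gives about 12.5 to 25 points of separation, with NAP .71 to .84 (ties half) or .41 to .68 (no tie credit). The upper end presumes set-level place knowledge. The bias shrinks with partial sharing and disappears with a fully shared pool.

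A reader might conclude that the control is invalid for this outcome, or that any location effect is guesswork. Neither follows: the place pool is unstated, and accuracy well above 25% would still show learning. Expressive labeling, the phase changes it drives and the conclusions based on it are unaffected. This is an inexpensive improvement to one secondary, interpretive outcome.

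**What to change.** Keep the no-teaching control and add the following for location:

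1. State how many places are used and whether the three sets share them.
2. Code the place named on every location trial from the existing video. No answer, or an answer that the child does not know, counts as a non-match.
3. Add to each location graph, for each taught set and session, the average match from re-pairing the child's four answers with the four objects (at most 25% when places within a set are distinct).
4. Claim object-location learning only where the taught set lies above both the control and this line. Judge this across sessions: with one-to-one guessing, a single session lies above the line in 7 of 24 cases (2 matches in 6, 4 matches in 1), or 29%.

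The cost is minor extra coding and one line per taught set on the location graphs. Some apparent location effects will become smaller, because remembering which places belong to a set is no longer credited as knowing which object goes where.
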